**LIST OF ABBREVIATIONS**

AE	Adverse event
AESI	Adverse Events of Special Interest
ChAd155-RSV	Investigational recombinant chimpanzee adenovirus Type 155-vectored RSV vaccine
CI	Confidence Interval
CMI	Cell-mediated immunity
CTRS	Clinical Trial Registry Summary
ERD	Enhanced RSV disease
ES	Exposed Set
GMC	Geometric mean antibody concentration
GMT	Geometric mean antibody titer
ICH	International Conference on Harmonisation
IDMC	Independent Data Monitoring Committee
iSRC	Internal Safety Review Committee
LL	Lower Limit of the confidence interval
LLOQ	Lower Limit of Quantification
LRTI	Lower respiratory tract infection
MedDRA	Medical Dictionary for Regulatory Activities
N.A.	Not Applicable
PCA	Palivizumab Competing Antibodies
PPS	Per Protocol Set
RR	Respiratory rate
RSV	Respiratory syncytial virus
RSV-Hd	High dose ChAd155-RSV vaccine ( $5 \times 10^{10}$ vp)
RSV-Ld	Low dose ChAd155-RSV vaccine ( $5 \times 10^9$ vp)
RSV-Md	Middle dose ChAd155-RSV vaccine ( $1.5 \times 10^{10}$ vp)
RSV-RTI	Respiratory tract infection associated with RSV infection
RTI	Respiratory tract infection
SAE	Serious adverse event
SAP	Statistical Analysis Plan
SD	Standard Deviation
SHS	Study Headline Summary

SR	Study Report
TFL	Tables Figures and Listings
TOC	Table of Content
UL	Upper Limit of the confidence interval

[figure not shown]
# 1. DOCUMENT HISTORY

Date	Description	Protocol Version
28-MAR-2018	Final version	Amendment 4 - 10-DEC-2017

# 2. STUDY DESIGN

Figure 1 Study design

Please note that for the analysis for D61, D366 and D731, the study will be converted in cDISC standard. To avoid confusion between analysis planned and table template, all the text and figures have been changed into cDISC, i.e. Day 'DX' is changed to Day 'DX+1'.

**Hd:** High dose; **IDMC:** Independent Data Monitoring Committee; **iSRC:** Internal Safety Review Committee; **Ld:** low dose; **Md:** middle dose; **RSV:** respiratory syncytial virus; **SCR:** Screening; **SE:** solicited events; **vp:** viral particles.  
 ‡ On Day 4 and Day 34, a visit may take place at the investigators clinical facility or the investigator/clinical staff may call the subjects' parent(s)/LAR(s), as appropriate to the circumstances in the judgment of the investigator.  
 a Surveillance for RSV-RTI comprises monthly nasal swab collected to detect asymptomatic RSV infections during RSV season and active and passive surveillance contacts for RSV symptomatic RTI (see Section 9.2 of the protocol). Data about RSV-RTI incidence will be reviewed monthly by an IDMC.  
 b Within each step, an iSRC will review all accumulating safety data three weeks after the start of vaccination and then about every three weeks (until the IDMC has reviewed all safety data up to 30 days after administration of Dose 2 in Step 3 i.e. Day 61). The IDMC will review all accumulating reactogenicity and safety data monthly throughout the period of vaccination (up to 30 days after administration of Dose 2 in Step 3, i.e. Day 61) and accumulating SAEs until Day 731. Refer to Sections 9.10.2 and 9.10.3 of the protocol.

- c Visit 2 (Day 2), Visit 4 (Day 8), Visit 6 (Day 32), Visit 8 (Day 38) and Visit 11 (Day 731) may take place in the subject's home or at the investigators clinical facility as appropriate to the circumstances in the judgment of the investigator.
- d Dose escalation will proceed after administration of two doses of the vaccine to 32 subjects in Step 1. However, in the absence of a significant safety concern detected in the regular monitoring of accumulating safety data on at least 16 subjects, the IDMC may allow for dose escalation to proceed without the requirement of enrolling and evaluating the full group size of 32 subjects. A subsequent dose escalation (from Step 2 to Step 3) will proceed after administration of two doses of the vaccine to between a maximum of 32 to a minimum of 16 subjects in the absence of a significant safety concern detected by the IDMC in the regular monitoring of accumulating safety data. Thus, upon review of the accumulating safety data on a minimum of 16 subjects after administration of two doses of the vaccine, the IDMC may decide that based on the evolving safety profile, sufficient information has been accumulated to allow safe progression to the next sequential dose level. It will be ensured that, as a minimum the IDMC will have reviewed safety data of at least 16 subjects for two doses and given their formal approval prior to enrolling subjects to the next dose level.
- e Only for hematology.
- f Day 8 hematology testing will be performed if any  $\geq$  Grade 1 for platelet decrease is detected on Day 1 after vaccination; to ensure its resolution. Similarly, hematology testing on Day 38 will be performed if any  $\geq$  Grade 1 for platelet decrease is detected on Day 32.
- g Refer to Section 6.6.11.3 of the protocol
- h The IDMC will perform a review when all safety data up to 30 days after administration of Dose 2 in Step 3 (i.e. Day 61) are available.
- i Blood samples for CMI and for humoral immunogenicity may be postponed until after the RSV serostatus is known and eligibility is confirmed up to or on Day 1 (but before vaccination).

- **Experimental design:** Phase I/II, observer-blind, randomized, placebo-controlled, multi-centric, study with two parallel groups per step in a 3-step staggered design
- **Duration of the study:** approximately 24 months:
  - Epoch 001: primary starting at the Screening visit and ending at Visit 9 (Day 61)
  - Epoch 002: follow-up starting at Visit 10 (Day 366) and ending at Visit 11 (Day 731)

Any safety, immunogenicity and disease surveillance data collected beyond Visit 9 (Day 61) will be collected in Epoch 002

- **Primary completion Date:** Visit 9 (Day 61).
- **End of Study:** Last testing results released of samples collected at Visit 11 (Day 731). \*

\* Up to Visit 11 (Day 731), there will be monthly nasal swab to detect asymptomatic RSV infections during the RSV season and if following active or a passive surveillance contacts, subject presents symptoms of RTI, a nasal swab will be collected.

- **Study groups:** Throughout the three steps, infants will be randomized in two groups to receive either ChAd155-RSV vaccine or placebo.

**Table 1 Study groups and epochs foreseen in the study**

Step	Study groups	Number of subjects*	Age (Min/Max)	Epochs	
				Epoch 001	Epoch 002
1	RSV-Ld	~ 16	12 months - 23 months	X	x
	Placebo-Ld	~ 16	12 months - 23 months	X	x
2	RSV-Md	~ 16	12 months - 23 months	X	x
	Placebo-Md	~ 16	12 months - 23 months	X	x
3	RSV-Hd	~ 16	12 months - 23 months	X	x
	Placebo-Hd	~ 16	12 months - 23 months	X	x

**RSV-Ld:** low dose ChAd155-RSV vaccine ( $5 \times 10^9$  vp); **RSV-Md:** middle dose ChAd155-RSV vaccine ( $1.5 \times 10^{10}$  vp);  
**RSV-Hd:** high dose ChAd155-RSV vaccine ( $5 \times 10^{10}$  vp).

\*The target will be to enroll up to 96 RSV-seropositive infants aged 12 to 23 months at the time of first vaccination (unless the dose escalation IDMC decision can be made based on the evaluation of accumulating safety data on fewer subjects) to ensure that at least 64 infants receive two doses of study vaccine (ChAd155-RSV or Placebo) (see Section **Error! Reference source not found.**). Then the number of subjects at each step will be at least 16 (approximately 8 subjects per group) at steps 1 and 2 and 32 (approximately 16 subjects per group at step 3)

- **Vaccination schedule:** two IM vaccine doses administered according to a 0, 1-month schedule (i.e. at Day 1 and Day 31)
- **Treatment allocation:** infants will be randomized using a randomization system on internet (SBIR) at first vaccination
- **Blinding:** observer-blind in Epoch 001 and single-blind in Epoch 002
- **Sampling schedule:**

Blood samples for biochemistry will be taken from all infants at Screening (up to 29 days before first vaccination to Day 1) and on Day 31, and Day 61 (refer to Table 11 of the protocol for the list of parameters to be tested). Blood samples for hematology will be taken from all infants at Screening (up to 29 days before first vaccination to Day 1) and on Day 1, Day 31, Day 32, and Day 61 (refer to Table 11 of the protocol for the list of parameters to be tested). Day 8 hematology testing will be performed if any  $\geq$  Grade 1 for platelet decrease is detected on Day 2 after vaccination, to ensure its resolution. Similarly, hematology testing on Day 38 will be performed if any  $\geq$  Grade 1 for platelet decrease is detected on Day 32. A clinical examination with special attention given to detection of spontaneous bleeding or easy bruising and evidence of bruising or petechiae will be performed by the investigator/study staff on Day 2, Day 4 and Day 8 after each vaccination (i.e. Day 2, Day 4, Day 8, Day 32, Day 34, and Day 38. The visits on Day 4 and Day 34 may be replaced by a phone call by the investigator/study staff to inquire of the infants' general health and to solicit reports of a rash, spontaneous bleeding or easy bruising. On Day 2, and Day 32, special attention will also be given to the detection of petechiae or evidence of petechiae induced by the tourniquet. This special attention to detection of petechiae or evidence of petechiae induced by the tourniquet will also be given on Day 8 and/or Day 38 in case hematology testing will be performed on that day. Further testing may be required to investigate a finding or guide subject management based on the investigators clinical judgment. Subjects' parent(s)/LAR(s) will be instructed to contact the investigator/study staff if their child presents symptoms of spontaneous bleeding or easy bruising or if their child develops a rash in the month following vaccination, in order to detect any thrombocytopenic petechiae or purpura. The

investigator will, based on his/her medical judgement, appropriately investigate infants with clinical suspicion of low platelets

- Blood sample for **RSV serostatus** will be taken from all infants at Screening.
- Blood samples for **CMI** are limited to those in investigational sites with a laboratory in proximity capable to perform WBS necessary for the CMI assay. In those sites, samples will be taken from all subjects at Screening and on Day 31, Day 61, and Day 366.

*Note: Blood samples for CMI taken on Day 8 and Day 38 for subjects enrolled under protocol amendment 1 will still be assessed for CMI.*

- Blood samples for **humoral immunogenicity** will be taken from all subjects at Screening and on Day 31, Day 61, and Day 366.
  - Blood sample for **assessment of mechanism of illness (potential ERD)** will be taken from subjects hospitalized for LRTI (only for RSV-positive subjects using a locally available RSV test).
  - Nasal swab: there will be monthly nasal swab to detect asymptomatic RSV infections during the RSV season and if following active or a passive surveillance contacts, a subject present symptom of RTI, a nasal swab will be collected.
- **Study visits:** Visit 1 (Day 1), Visit 5 (Day 31), Visit 9 (Day 61) and Visit 10 (Day 366) must be performed at the investigators clinical facility. Visit 2 (Day 2), Visit 4 (Day 8), Visit 6 (Day 32), Visit 8 (Day 38) and Visit 11 (Day 731) (no blood sampling for immune response and no vaccine administration) may take place in the subject's home or at the investigators clinical facility as appropriate to the circumstances in the judgment of the investigator. Visit 3 (Day 4) and Visit 7 (Day 34) may take place at the investigators clinical facility or the investigator/clinical staff may call the subjects' parent(s)/LAR(s), as appropriate to the circumstances in the judgment of the investigator.
  - **Surveillance for RSV-RTI, difficulty in breathing and wheezing episodes.**  
Surveillance period will be carried out from Visit 1 (after Dose 1) until Visit 11 (Day 731). In order to detect asymptomatic RSV-RTI, monthly nasal swabs for analysis at sponsor laboratory will be performed for all subjects during the RSV season. In order to timely detect RSV-RTI and to ensure cases are timely captured by the study sites, both active and passive surveillance will be conducted:
    - **Passive surveillance:** Parent(s)/LAR(s) are instructed to contact the investigator/study staff as soon as the subject experiences new RTI symptoms (cough, runny nose or blocked nose) or worsening of RTI symptoms, or in case of difficulty in breathing or wheezing.
    - **Active surveillance:** parent(s)/LAR(s) of all the subjects will be contacted by the investigator/study staff on a regular basis (weekly during the RSV season and every month outside the RSV season) to identify any potential RSV-RTI and to remind the parent(s)/LAR(s) of the subjects to report any new occurrence of RTI symptoms (cough, runny nose, blocked nose) or worsening of RTI symptoms, or in case of difficulty in breathing or wheezing as soon as possible.

### **3. OBJECTIVES**

#### **3.1. Primary objective**

- To evaluate the safety and reactogenicity of three dose levels of the RSV investigational vaccine when administered as two IM doses according to a 0, 1-month schedule, up to 30 days after Dose 2 (i.e. Day 61) in RSV-seropositive infants aged 12 to 23 months

#### **3.2. Secondary objectives**

- To evaluate the safety of two IM doses of three dose levels of the RSV investigational vaccine when administered according to a 0, 1-month schedule from study start (Day 1) up to study conclusion (Day 731) in RSV-seropositive infants aged 12 to 23 months
- To evaluate the occurrence of RSV respiratory tract infections in RSV-seropositive infants from Visit 1 (Day 1, after Dose 1) up to study conclusion (Day 731)
- To evaluate the magnitude of the CMI induced by two IM doses of three dose levels of the RSV investigational vaccine when administered according to a 0, 1-month schedule, up to Day 366 in RSV-seropositive infants aged 12 to 23 months.
- To evaluate the humoral immunogenicity induced by two IM doses of three dose levels of the RSV investigational vaccine when administered according to a 0, 1-month schedule, up to Day 366 in RSV-seropositive infants aged 12 to 23 months

#### **3.3. Tertiary objectives**

- To further evaluate the CMI profile induced by two IM doses of three dose levels of the RSV investigational vaccine when administered according to a 0, 1-month schedule, up to Day 366 in RSV-seropositive infants aged 12 to 23 months
- If deemed necessary, to further characterize the immune response of the RSV investigational vaccine when two IM doses are administered according to a 0, 1-month schedule in RSV-seropositive infants.

### **4. ENDPOINTS**

#### **4.1. Primary endpoints**

- Occurrence of AEs from first vaccination (Day 1) up to Day 61.
  - Occurrence of each solicited local and general AE, during a 7-day follow-up period after each vaccination (i.e. the day of vaccination and 6 subsequent days).
  - Occurrence of any unsolicited AE, during a 30-day follow-up period after each vaccination (i.e. the day of vaccination and 29 subsequent days).

- Occurrence of any SAE from Day 1 up to Day 61.
- Occurrence of episode of spontaneous or excessive bleeding (AE of specific interest), during a 30-day follow-up period after each vaccination.
- Occurrence of any hematological (hemoglobin level, white blood cells and platelets) laboratory abnormalities at Screening, Day 1, Day 8, Day 31, Day 32, Day 38, and Day 61.
- Occurrence of any biochemical (alanine aminotransferase, aspartate aminotransferase and creatinine) laboratory abnormalities at Screening, Day 31, and Day 61

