1.2.4.3. Rationale for monitoring of hematology parameters

Emphasis on “minimal risk” is imperative for the protection of the pediatric population participating to research studies where blood sample volume limits is a critical parameter. To stay within blood sampling limits that are consistent with physiological “minimal risk” in this young and vulnerable population, but also to minimize any development of needle aversion, blood draws for the determination of hematological parameters are scheduled at Day 1 and Day 31 (corresponding to the first day after administration of the vaccine). Additional specimens will be drawn if any \geq Grade 1 for platelet decrease is detected at Day 1 or Day 31 to investigate clinical symptoms suggestive of low platelets. Blood samples collected within the screening window will serve as baseline for the immunological analysis and for the hematology and biochemistry check-up before vaccination. Consequently, the maximum blood draw volumes collected per protocol have been restricted to 9.0 mL within 24 hours and 26.2 mL over eight weeks (refer to [Table 5](#) and [Table 7](#)). For investigational sites without a laboratory in proximity capable to perform whole blood stimulation [WBS] necessary for the CMI assay the volumes will be less. Of note, it is considered that blood sample volumes ranging from 1 to 5% of total blood volume within 24 hours and up to 10% of total blood volume over 8 weeks are consistent with the limited evidence available on the minimal physiological risk for healthy children [[Howie](#); 2011]. The total blood volume of a child is around 75 to 80 mL/kg (85 to 105 mL/kg in the neonatal period). Considering a girl of 12 months of age with a low weight of 7.3 kg (5th percentile [[WHO](#); 2006]), the minimal individual total blood volume in the study population would be 547.5 mL and therefore the safer limits of blood draw volumes would range from 5.5 to 27.4 mL within 24 hours and be limited to 54.7 mL over 8 weeks. To minimize any development of needle aversion, pain relief by means of a topical local anesthetic may be offered to infants prior to any blood sampling requested by the protocol at the discretion of the investigator.

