11. STATISTICAL METHODS

11.1. Primary endpoint

- Occurrence of AEs from first vaccination (Day 0) up to Day 60.
 - Occurrence of each solicited local and general AE, during a 7-day follow-up period after each vaccination (i.e. the day of vaccination and 6 subsequent days).
 - Occurrence of any unsolicited AE, during a 30-day follow-up period after each vaccination (i.e. the day of vaccination and 29 subsequent days).
 - Occurrence of any SAE from Day 0 up to Day 60.
 - Occurrence of episode of spontaneous or excessive bleeding (AE of specific interest), during a 30-day follow-up period after each vaccination.
 - Occurrence of any hematological (hemoglobin level, white blood cells and platelets) laboratory abnormalities at Screening, Day 1, Day 7, Day 30, Day 31, Day 37, and Day 60.
 - Occurrence of any biochemical (alanine aminotransferase, aspartate aminotransferase and creatinine) laboratory abnormalities at Screening, Day 30, and Day 60.

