11.8. Analysis of safety

11.8.1. Within groups assessment

The analysis will be performed on the TVC.

The percentage of subjects with at least one **local AE** (solicited and unsolicited), with at least one **general AE** (solicited and unsolicited) and with any AE during the 7-day or 30-day follow-up period will be tabulated with exact 95% CI after each vaccine dose and overall (**Amended 10 December 2017**). The percentage of doses followed by at least one local AE (solicited and unsolicited), by at least one general AE (solicited and unsolicited) and by any AE during the 7-day or 30-day follow-up period will be tabulated, overall vaccination course, with exact 95% CI. The same computations will be done for Grade 3 AEs, for any AEs considered related to vaccination and for any Grade 3 AEs considered related to vaccination.

The percentage of subjects reporting each individual **solicited local AE** (any grade, Grade 2, Grade 3, resulting in a medically attended visit) and **solicited general AE** (any grade, Grade 2, Grade 3, any related, Grade 2 related, Grade 3 related, resulting in medically attended visit) during the 7-day follow-up period (Day 0-6) will be tabulated for each group after each vaccine dose and overall. Similarly, the percentage of doses followed by each individual solicited local and general AE and their sub-categories, will be tabulated, overall vaccination course, with exact 95% CI.

For fever, the number and percentage of subjects reporting fever by half degree (°C) cumulative increments during the 7-day follow-up period (Day 0-6) will be tabulated for each group after each vaccine dose and overall. Similar tabulations will be performed for any fever with a causal relationship to vaccination, Grade 3 (> 39.5°C) causally related fever and for any fever resulting in a medically attended visit. In addition, the prevalence of any and Grade 3 fever will be presented graphically over time after vaccination.

For each group and for each **hematology and biochemistry** parameter:

- The percentage of subjects having hematology and biochemistry results below or above the local laboratory normal ranges will be tabulated by timepoint.

The maximum grading from Screening up to Visit 9 (Day 60) will be tabulated (Refer to [Appendix C](#)).

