The percentage of subjects with unsolicited AEs within 30 days (Day 1-30) after each vaccine dose (overall doses) with its exact 95% CI will be tabulated by group and by MedDRA preferred term. Similar tabulation will be done for Grade 3 unsolicited AEs, for any causally related unsolicited AEs, for Grade 3 causally related unsolicited AEs and for unsolicited AEs resulting in a medically attended visit. The verbatim reports of unsolicited AEs will be reviewed by a physician and the signs and AEs will be coded according to the MedDRA Dictionary Version 20 for Adverse Reaction Terminology. Every verbatim term will be matched with the appropriate Preferred Term.

The percentage of subject with episode of spontaneous or excessive bleeding (AE of specific interest), during a 30-day follow-up period after each vaccination will be tabulated by group according to associated PT code presented in Section 12. The percentage of subjects with RSV-LRTI (AE of specific interest) from Dose 1 up to Day 365 and from Dose 1 up to study conclusion (Day 730) will be tabulated by group according to associated PT code presented in Section 12.

The percentage of subjects with SAE within 30 days (Day 1-30) after each vaccine dose with its exact 95% CI will be tabulated by group and by MedDRA preferred term. Similar table will be generated for SAE from Dose 1 up to Day 61, from Dose 1 up to Day 366 and from Dose 1 up to Day 731.

SAEs reported throughout the study and AE of specific interest will be described in detail.

The percentage of subjects using concomitant medication (any medication, any antipyretic/ analgesic and any antipyretic taken prophylactically, respectively) during the 7-day follow-up period (Day 1-7) and during the 30-day follow-up period (Day 1-30) will be summarized by group after each vaccine dose and overall.

For each group and for each hematology and biochemistry parameter:

- The percentage of subjects having hematology and biochemistry results below/above/within the local laboratory normal ranges will be tabulated by timepoint and toxicity grading scale.
- The maximum grading from Screening up to Visit 9 (Day 61) will be tabulated by grading the safety laboratory values according to toxicity criteria Grading scale adapted from [Division of AIDS, 2003], [Division of AIDS, 2004] and [Division of AIDS, 2007].

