## 9. CHANGES FROM PLANNED ANALYSES

Following are the changes in the planned analysis:-

- The naming of the cohort has been changed per cDISC standards.
- Per cDISC standard, the day of first vaccination is now changed from Day 0 to Day 1.
- The study design diagram has been adapted as per cDISC format
- In secondary endpoints, specific safety endpoints for Day 1 up to D366 has been added as follows: -
  - Occurrence of SAEs from study start (Day 1) up to Day 366.
  - Occurrence of RSV-LRTI (AE of specific interest) as from Dose 1 administration up to Day 366.
  - Occurrence of RSV-RTI, RSV-LRTI, severe RSV-LRTI (according to standardized case definitions) as from Dose 1 administration up to Day 366.
- For the immunogenicity analysis, the analysis will be performed on both PPS and ES without any condition on percentage of subjects excluded
- For inclusion of subjects in PPS for analysis of immunogenicity, subjects should have received both the doses and not atleast one dose.

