**<each group>:**

RSV-Ld = Low dose ChAd155-RSV vaccine (5 x 10^9 vp)  
 RSV-Md = Middle dose ChAd155-RSV vaccine (1.5 x 10^10 vp)  
 RSV-Hd = High dose ChAd155-RSV vaccine (5 x 10^10 vp)  
 Placebo-Ld = Non-active control (0.5 ml)  
 Placebo-Md = Non-active control (0.15 ml)  
 Placebo-Hd = Non-active control (0.5 ml)  
 N = number of subjects with available results for the specified laboratory parameter and timing in a given baseline category  
 n/% = number/percentage of subjects in the specified category  
 Below = below the normal laboratory range defined for the specified laboratory parameter  
 Within = within the normal laboratory range defined for the specified laboratory parameter  
 Above = above the normal laboratory range defined for the specified laboratory parameter  
 SCR= Screening  
 PI (D2): Post-vaccination dose 1 at Day 2  
 PI (D8): Post-vaccination dose 1 at Day 8  
 PI (D31): Post-vaccination dose 1 at Day 31  
 PII (D32): Post-vaccination dose 2 at Day 32  
 PII (D38): Post-vaccination dose 2 at Day 38

PII (D61): Post-vaccination dose 2 at Day 61  
 UNSCH: Unscheduled visit for safety

**Template 25 Summary of hematology and biochemistry results by maximum grade from VISIT X (DX) up to VISIT Y (DY) – post dose 1 of vaccination versus baseline <Exposed Set>**

Laboratory parameter	Baseline (SCR)	Visit 2 to Visit X	<each group >		
			N	n	%
Hemoglobin (decrease)	Unknown	Unknown			
		Grade 0			
		Grade 1			
		Grade 2			
		Grade 3			
		Grade 4			
	Grade 0				
	Grade 1				
	Grade 2				
	Total				
Leukocytes (White Blood Cells) (decrease)	...				
Neutrophil (decrease)					
Platelets					
Alanine Aminotransferase					
Aspartate Aminotransferase					
Creatinine					

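### The SAP's primary haematology endpoint says Day 1 where its own numbering requires Day 2, and both documents let a pre-vaccination Screening grade stand as the maximum grade

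*SAP*

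**What the plan says.** **Day numbering.** SAP section 2 states the conversion: "Day 'DX' is changed to Day 'DX+1". SAP section 9 lists it among the changes: "Per cDISC standard, the day of first vaccination is now changed from Day 0 to Day 1".

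**Haematology time points.** Protocol 11.1, in protocol numbering, lists "laboratory abnormalities at Screening, Day 1, Day 7, Day 30, Day 31, Day 37, and Day 60". SAP 4.1, in SAP numbering, lists "laboratory abnormalities at Screening, Day 1, Day 8, Day 31, Day 32, Day 38, and Day 61". The SAP sampling schedule in section 2 also gives Day 1 as the first haematology draw after Screening.

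**Maximum grade.** Protocol 11.8.1: "The maximum grading from Screening up to Visit 9 (Day 60) will be tabulated". SAP 6.4.1.1: "The maximum grading from Screening up to Visit 9 (Day 61) will be tabulated", using the toxicity grading scale.

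**Mock tables.** The footnote to SAP Template 24 reads "PI (D2): Post-vaccination dose 1 at Day 2", and Template 26 also has a D2 row. Template 25 takes Screening as baseline and shows the maximum grade from Visit 2 onward against it.

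**The concern.** There are two faults, and they differ in origin.

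The first belongs to the SAP. In its numbering, Day 1 is the vaccination day. Read literally, the primary endpoint names a day without a scheduled haematology sample and does not name the 24-hour sample after Dose 1, although it keeps the matching sample after Dose 2 (Day 32). That sample has a specific purpose. Protocol 1.2.4.3 says the acute draws are "scheduled at Day 1 and Day 31 (corresponding to the first day after administration of the vaccine" and explains that the platelet fall in rabbits was greatest at 24 hours. Protocol 11.4 treats thrombocytopenia as the safety concern identified in advance.

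The second is shared. The laboratory endpoint sits under adverse events counted from the first vaccination, but Screening comes before any dose and serves as the baseline check. If the maximum runs from Screening, a grade that no dose could have caused enters the table, and an infant whose abnormality predates vaccination looks the same as one whose abnormality followed it.

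**Working it through.** No power or error-rate figure is involved. The check is a day-by-day conversion and a reading of the maximum-grade rule.

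**1. Conversion.** Rule from SAP section 2: SAP day = protocol day + 1. Inputs: the lists in Protocol 11.1 and SAP 4.1.

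| Protocol day | + 1 | SAP 4.1 says | Match |
|---|---|---|---|
| 1 | 2 | 1 | no |
| 7 | 8 | 8 | yes |
| 30 | 31 | 31 | yes |
| 31 | 32 | 32 | yes |
| 37 | 38 | 38 | yes |
| 60 | 61 | 61 | yes |

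Biochemistry: 30 + 1 = 31 and 60 + 1 = 61, both as stated. The slip is in one haematology day.

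**2. What SAP Day 1 is.** Converting back, 1 − 1 = protocol Day 0, which is Visit 1. Protocol Table 5 schedules haematology at Screening and Visits 2, 4, 5, 6, 8 and 9, and not at Visit 1.

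**3. Whether the change was intended.** SAP section 9 lists no change to the haematology time points. The SAP sampling paragraph gives Day 1 for the draw but Day 2 for the platelet result that triggers the Day 8 test. Footnote f of SAP Figure 1 gives Day 1 for that trigger and the converted Day 32 for its counterpart after Dose 2. This is an incomplete conversion.

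**4. Which sample the label concerns.** Haematology samples planned for every infant after vaccination starts are SAP Days 2, 31, 32 and 61; Days 8 and 38 are conditional. Day 2 is the only unconditional acute sample after Dose 1. The next routine draw is 31 − 2 = 29 days later.

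**5. The maximum-grade rule.** Consider four hypothetical infants and one parameter:

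| Screening grade | Highest grade, Visit 2 to Visit 9 | Text rule (from Screening) | Template 25 (baseline → maximum) |
|---|---|---|---|
| 1 | 0 | 1 | 1 → 0 |
| 0 | 1 | 1 | 0 → 1 |
| 1 | 1 | 1 | 1 → 1 |
| 1 | 2 | 2 | 1 → 2 |

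Under the text, the first three histories give the same entry. Template 25 separates them. The first infant is misplaced: no abnormality after vaccination, but a tabulated maximum of Grade 1.

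**6. How far carry-over can go.** Protocol 5.3 excludes infants with any Grade 2 or higher, or clinically significant Grade 1, laboratory abnormality at the last screening sample. What remains is a Grade 1 result judged not significant, for example haemoglobin of 9.0 to below 10.5 g/dL (Protocol Appendix C). Such a result can raise the Grade 1 count and lower the Grade 0 count. It leaves Grades 2 to 4 essentially untouched.

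**The case against.** **The 24-hour data are not lost.** A reader might infer from SAP 4.1 that this sample drops out of the analysis. The documents do not support that. SAP 11.1 repeats the conversion and says the analysis will adjust for it. Templates 24 and 26 have D2 rows, Template 25 starts at Visit 2, and no haematology sample is scheduled on SAP Day 1 that could produce a rival result. This stands: the fault lies in the endpoint and sampling text. But SAP section 13 calls the mock tables illustrative. Template 24 even shows alanine aminotransferase at D2 and D8, when no biochemistry is scheduled. Such shells should not have to correct a primary endpoint.

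**Day 1 is not free of blood sampling.** A reader might infer that it is. Postponed baseline immunogenicity blood may be taken that day before vaccination; only haematology is unscheduled.

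**Screening comes from the protocol.** True. The SAP follows the protocol's synopsis and section 11.1, so both documents need correcting.

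**The remedy is largely planned.** SAP 6.4.1.1 also tabulates results against normal ranges by time point, and Template 25 is already the right table. This stands, but it leaves text and table describing different analyses.

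**No decision depends on it.** The between-group intervals in SAP 6.4.1.2 cover Grade 2/3 adverse events, fever and related serious events. Holding rule 2c uses Grade 3 or higher abnormalities, and the escalation platelet analysis uses protocol Day 31 counts. This stands.

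**Conclusion.** Both faults are real and modest. One of six haematology study days in the SAP's primary endpoint is mislabelled, and the sampling text repeats it. It concerns the sample most relevant to the platelet concern, but the planned tables would probably report that sample anyway. The maximum-grade sentence in both documents, if followed, gives a table that counts grades from before vaccination, under an endpoint that starts at vaccination, and disagrees with Template 25. The effect is confined to the descriptive Grade 1 rows and the corresponding Grade 0 counts, provided the screening exclusions are applied as written.

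Three stronger readings are not supported. A reader might infer that treatment differences would be materially diluted. The documents give no prevalence of non-significant Grade 1 results at Screening, and the chance of finding at least one such infant in an arm would not measure bias; carry-over would be expected in both randomised arms alike. A reader might also infer that a re-screened infant's failed first sample would enter the table. No text says so, and eligibility rests on the last screening sample. Nor does the day error extend to biochemistry, whose days are converted correctly.

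**What to change.** 1. In SAP 4.1 and the SAP section 2 sampling text, change Day 1 to Day 2 for haematology. Align footnote f of SAP Figure 1 with the same numbering.
2. In the laboratory endpoints of both documents, haematology and biochemistry alike, treat the last pre-vaccination Screening result as baseline and not as an occurrence.
3. In SAP 6.4.1.1 and Protocol 11.8.1, define the maximum grade as the highest from Visit 2 (SAP Day 2) to Visit 9 (SAP Day 61), cross-tabulated against baseline grade as in Template 25.
4. Record the clarification in SAP section 9. Protocol 11.12 already requires changes from the planned analysis to be described and justified in the final report.

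The cost is wording only. No new data, visits or samples are needed, and Template 25 already provides the layout.
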